6.1.5 Analysis Methods

There will be no formal statistical testing unless indicated otherwise.

A summary will be provided for the following TEAEs per period and overall (Table 14.3.1.1.1-14.3.1.1.3):

- Subjects with Any TEAE
- Subjects with Any Study Drug-Related¹ TEAE
- Subjects with Any TEAE with an Outcome of Death
- Subjects with Any Serious TEAE
- Subjects with Any Study Drug-Related Serious TEAE
- Subjects with Any TEAE Leading to Discontinuation of Study Drug
- Subjects with Any Study Drug-Related TEAE Leading to Discontinuation of Study Drug
- Subjects with Any TEAE of Special Interest
- Subjects with Any Study Drug-Related TEAE of Special Interest

The adverse events will be shown by MedDRA system organ class and preferred term, in order of descending overall frequency. For each AE, the percentage of subjects who experience at least 1 occurrence of the given event will be summarized per period and overall. Incidence tabulations will be provided for overall summary (Table 14.3.1.2.1-14.3.1.2.3), summary by highest severity (Table 14.3.1.3.1-14.3.1.3.3), and summary by relatedness (Table 14.3.1.4.1-14.3.1.4.3).

Incidence of Serious TEAEs, TEAEs of Special Interest, TEAEs Leading to Subject Withdrawal and TEAEs Leading to Death will be tabulated by MedDRA System Organ Class and Preferred Term (Table 14.3.1.5.1-14.3.1.5.4), and listed as well (Listing 14.3.1.6.1-14.3.1.6.4).

Adverse events with preferred terms associated with blood pressure changes will also be presented by infusion period, SOC, PT, and treatment group. Infusion

period will be further categorized by whether the event start date occurred during the infusion period or after the infusion period. Examples of such events can be identified by the following preferred terms: blood pressure decreased, blood pressure diastolic decreased, blood pressure systolic decreased, blood pressure increased, increased blood pressure, blood pressure diastolic increased, blood pressure systolic increased, hypotension, hypertension, low blood pressure, high blood pressure. This is a non-exhaustive list and a review of AE MedDRA coding will be conducted prior to lock to identify all events associated with blood pressure changes. (Table 14.3.1.7.1-14.3.1.7.3).

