The infusion duration for all subjects will be between 2 hours to a maximum of 3 hours to maintain blinding. Flow rates will be titrated according to dose-specific guidelines to ensure that the entire assigned dose is administered during this interval. The following measures will be taken to ensure adequate allocation concealment during infusions: blinding of subjects, trial partners, study coordinators, physicians, and cognitive test administrators to treatment dose; use of blinded Outcomes Assessors and unblinded Infusion Nurses; standard time for attachment to the IV infusion setup (up to 180 minutes); and measures to block view of vial(s) and infusion pump throughout the infusion.

All subjects will undergo a screening visit, baseline visit, treatment visits, follow-up visits and an end of study/early termination visit. During each 5-day dosing period, subjects will reside in inpatient units to facilitate safety evaluation. Subjects will be discharged from the inpatient facility the day after the 5th day of dosing. Safety and tolerability assessments will occur at every visit. Neurocognitive and motor assessments will be performed at baseline and at periodic interim visits following dosing. Subjects who are eligible and consent to participate in the optional cerebrospinal fluid (CSF) biomarker research will undergo two lumbar punctures for CSF collection, the first occurring prior to initial dosing, and the second occurring following final dosing.

Objectives: The primary objective of the study is to assess the safety, tolerability, and feasibility of 2 dose levels of GRF6019 in subjects with mild to moderate AD. As a secondary objective, the study will assess the potential effects on cognition of the 2 dose levels using various cognitive measures. The exploratory objectives include changes on MRI and analysis of blood and CSF for specific biomarkers associated with AD.

Endpoints: Primary endpoints will be assessed as follows:

- Incidence of treatment-emergent adverse events (AEs) identified by MedDRA preferred term (PT) and grouped by MedDRA System Organ Class.
- Feasibility and tolerability of each dose level.

Secondary efficacy endpoints will be assessed as follows:

- Changes in scores on the Mini-Mental State Examination (MMSE).
- Changes in scores on the 11-item Alzheimer’s Disease Assessment Scale-Cognitive Subscale (ADAS-Cog/11).
- Changes in scores on the Grooved Pegboard Test.
- Changes in scores on the Category Fluency Test (CFT).

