2.3 POTENTIAL RISKS AND BENEFITS

2.3.1 KNOWN POTENTIAL RISKS

Collected human plasma may be used as a therapeutic product (known as “plasma” or “fresh frozen plasma”) or as source material for the production of pharmaceutical fractionated products (known as “plasma products” or “plasma derivatives”) ([Burnouf 2007](#)). GRF6019, a [REDACTED] human plasma protein fraction, [REDACTED] serves as a viable source of soluble, infusible plasma proteins from [REDACTED] healthy donors.

[REDACTED]

ABO antigen typing is not required prior to administration. Finally, the additional steps taken during production to remove viral pathogens provide an increased margin of pathogen safety in comparison to fresh frozen plasma.

[REDACTED] GRF6019 is not expected to significantly alter the urinalyses of recipients, their bleeding times, coagulation times, prothrombin times, prothrombin consumption, platelet counts or fibrinogen levels when given in quantities of up to 1000 mL. Hypotension may occur, particularly following rapid infusion or intraarterial administration to patients on cardiopulmonary bypass. The blood pressure may normalize spontaneously after the slowing or discontinuation of the infusion. [REDACTED]

[REDACTED]

GRF6019 is made from human plasma and may carry a risk of transmitting infectious agents, e.g., viruses, the variant Creutzfeldt-Jakob disease (vCJD) agent, and, theoretically, the Creutzfeldt-Jakob disease (CJD) agent. The risk that GRF6019 can transmit an infectious agent has been reduced by screening plasma donors for prior exposure, testing donated plasma, and including manufacturing steps with the capacity to inactivate and/or remove pathogens.

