6.1.5 DOSING AND ADMINISTRATION

The study agent will be infused in accordance with the Infusion Administration Manual provided to sites. The purpose of the Infusion Administration Manual is to promote safe administration of GRF6019 and maintain appropriate blinding of staff and study subjects. The manual will include provisions for masking study agent and concealing the IV apparatus from view of blinded staff and study subjects during the Infusion Period.

The study agent and dose to be administered will be provided by an unblinded pharmacist (or other qualified personnel responsible for drug accountability) to an unblinded Infusion Nurse. Administration of the study agent will be performed by the unblinded Infusion Nurse, and study outcome measures (including AEs and vital signs) will be assessed by a blinded Outcomes Assessor.

Infusion Nurses will be qualified by training and experience to administer infusions under the direction of the Principal Investigator. Only authorized Infusion Nurses may administer the study agent, and only subjects enrolled in the study may receive the study agent in accordance with applicable regulatory requirements.

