1 INTRODUCTION

This statistical analysis plan (SAP) describes the planned statistical analyses for the study entitled “A Prospective, Randomized, Double-Blind, Dose-Comparison Concurrent Control Study to Assess the Safety and Tolerability of GRF6019 Infusions in Subjects with Mild to Moderate Alzheimer’s Disease” (V6.0 12OCT2018, V7.0 02NOV2018). Analysis related to exploratory objectives (assessment of changes in composition and distribution of blood-based and CSF (in consenting subjects) biomarkers, as well as changes in imaging results as measured by vMRI, fMRI, and ASL) will be described in a separate plan. Mock shells for the CSR Appendix 14 are also produced as a separate working document to facilitate programming of Tables, Figures, and Listings (TFLs) according to the finalized SAP. The SAP is to be interpreted in conjunction with the protocol. If the final clinical study report contains changes to any planned statistical analyses, the justification for any such differences will be fully documented in the CSR.

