6.1.3 Period Allocation of AE

Adverse events are allocated to a period based on their start date and time. If the start date and time of an event falls between (or on) the start and stop date and time of a period, the AE is attributed to that period (treatment-emergent principle).

Rule: period start datetime \leq AE start datetime \leq period stop datetime.

In case of partial AE start dates and or times, the events are allocated to the periods using the available partial information on start and end datetime; no imputation will be done. If, for instance, for the AE start date only month and year are available, these data are compared to the month and year information of the periods. This rule may lead to multiplication of the event as a consequence of its assignment to multiple periods. In case of a completely missing AE start date, the event is allocated to the first period, except if the end date of the AE falls before the start of this period. In case of any other missing scenarios, the period allocation of AE will be determined by manual data review prior to database lock.

6.1.4 Variables Attributed to Adverse Events:

- AE term (verbatim and MedDRA preferred term and system organ class)
- Onset datetime, End datetime, and duration of AE
- Serious AE (Yes/No), if yes classification will be listed
- Severity (Mild, Moderate, Severe)
- Relation to study treatment (Unrelated, Possibly Related, Definitely Related)
- Frequency (Single Episode, Intermittent, Continuous)
- Action taken with study treatment (No Action Taken, Treatment Held, Treatment Discontinued)
- Other Action due to AE (Medication Therapy, Non-Drug Therapy, Other)
- Outcome of AE (Recovered/Resolved, Not Recovered/Not Resolved, Resolved/Resolved with Sequelae, Fatal, Unknown)
- AE leading to death (Yes/No)
-
- AE of special interest

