Table 14.3.1.7.1	Incidence of Treatment-Emergent Adverse Events (TEAEs) for Preferred Terms Associated with Blood Pressure Changes by MedDRA System Organ Class and Preferred Term	SAF
Table 14.3.1.7.2	Incidence of Treatment-Emergent Adverse Events (TEAEs) for Preferred Terms Associated with Blood Pressure Changes by MedDRA System Organ Class and Preferred Term in Period 1	SAF
Table 14.3.1.7.3	Incidence of Treatment-Emergent Adverse Events (TEAEs) for Preferred Terms Associated with Blood Pressure Changes by MedDRA System	SAF

Number	Title	Population
	Organ Class and Preferred Term in Period 2	
Table 14.3.2.1.1	Changes in hematology measurements	SAF
Table 14.3.2.1.2	Changes in serum chemistry measurements	SAF
Table 14.3.2.1.3	Changes in urinalysis measurements	SAF
Table 14.3.2.2	Frequency of categorical laboratory assessments	SAF
Table 14.3.2.3.1	Shift Table in hematology measurements	SAF
Table 14.3.2.3.2	Shift Table in serum chemistry measurements	SAF
Table 14.3.2.3.3	Shift Table in urinalysis measurements	SAF
Table 14.3.3.1	Changes from baseline in vital sign measurements and weight	SAF
Table 14.3.3.2	Changes from pre-dose in vital sign measurements within each infusion day	SAF
Table 14.3.3.3	Blood pressure measurements of special interest	SAF
Table 14.3.4.1	Changes from baseline in ECG measurements	SAF
Table 14.3.4.2	Frequency of overall ECG results	SAF
Table 14.3.5.1	Frequency of abnormal physical examination results	SAF
Table 14.3.5.2	Shift Table in physical examination results	SAF
Table 14.3.6	Frequency of Columbia-Suicide Severity Rating Scale (C-SSRS) Since Last Visit	SAF

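### SAP 6.1.5 sorts blood-pressure adverse events into during or after an undefined infusion period by start date, so its tables cannot isolate events that begin while the infusion is running

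*SAP*

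**What the plan says.** SAP 6.1.5 adds a special tabulation to the general adverse event tables: "Adverse events with preferred terms associated with blood pressure changes will also be presented by infusion period, SOC, PT, and treatment group". Events are then further "categorized by whether the event start date occurred during the infusion period or after the infusion period". The results go to Tables 14.3.1.7.1 (overall), 14.3.1.7.2 (Period 1) and 14.3.1.7.3 (Period 2). The second is titled in SAP section 10 as covering "Blood Pressure Changes by MedDRA System Organ Class and Preferred Term in Period 1".

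Section 6.1.5 does not say what the infusion period is. SAP section 1 states: "The SAP is to be interpreted in conjunction with the protocol". The protocol uses the capitalised term for the single daily infusion: section 6.1.5 speaks of "concealing the IV apparatus from view of blinded staff and study subjects during the Infusion Period", and section 10.6.1 has the nurse return used vials to the pharmacy when it ends. The Protocol Summary gives its length: "The infusion duration for all subjects will be between 2 hours to a maximum of 3 hours to maintain blinding". The version 7.0 revision history places the term in the List of Definitions with the same 2 to 3 hours.

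Elsewhere the SAP works with times. Section 6.1.3 allocates adverse events to study periods by comparing start datetime with the period's start and stop datetimes, and section 6.1.4 lists "Onset datetime, End datetime, and duration of AE" among the event variables. Protocol 8.4.1 requires only the date of onset.

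**The concern.** The protocol names an acute haemodynamic risk in section 2.3.1: "Hypotension may occur, particularly following rapid infusion". Both doses are given within the same 2 to 3 hour range, so the 250 mL arm is on average infused faster than the 100 mL arm. Tables 14.3.1.7.1 to 14.3.1.7.3 are the only planned adverse event tables that split events by their timing relative to the infusion. TEAE incidence is a primary endpoint, and a reader will look at the during rows to see whether blood-pressure events cluster in the infusion and differ by dose.

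The rule as written drops the time of day. Take a subject whose blood pressure falls mid-infusion on Day 3, another with a high reading that morning before the infusion, and a third with an event late that evening. All three events carry the same start date and land in the same cell. The during category then no longer means what its label says, and a delayed same-day effect is missing from the after category. Two programmers could also read the undefined term differently and produce different tables.

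**Working it through.** The plan gives no figure to reproduce. The check compares the two possible meanings of the term and then sizes the effect.

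**Reading A: the daily infusion (protocol sense).** The infusion lasts 2 to 3 hours.
- Share of a calendar day: 2/24 = 8.3%; 3/24 = 12.5%.
- A rule that sees only the date therefore widens the during window from 2–3 hours to 24 hours.
- One limit: SAP 6.1.2 makes an event before the first dose on Day 1 pre-treatment, so it is not in these tables. Pre-infusion events on later dosing days are.

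**Reading B: the dosing block (suggested by the Period 1 and Period 2 tables).** Five infusions are given over five days, or six with the grace day.
- Infusion hours per block: 5 × 2 = 10 to 5 × 3 = 15.
- Share of five calendar days: 10/120 = 8.3% to 15/120 = 12.5%. Share of six days: 10/144 = 6.9% to 15/144 = 10.4%.
- A date separates block from follow-up adequately, apart from later events on the last infusion day. But no cell isolates events that start while the infusion runs.

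These are shares of time, not of events. The documents give no distribution of onset times.

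**Average infusion rates (volume divided by duration).**
- 100 mL: 100/3 = 33.3 to 100/2 = 50 mL/h.
- 250 mL: 250/3 = 83.3 to 250/2 = 125 mL/h.
- Ratio at equal duration: 250/100 = 2.5. Across the permitted range: 83.3/50 = 1.7 to 125/33.3 = 3.75.

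**Illustration of the dilution (all risks assumed, none from the documents).** Let the true in-infusion risk be p = 5% at 100 mL and 30% at 250 mL. Let q be the risk, equal in both arms and independent, of a blood-pressure event at another time within the same category. The pooled risk is 1 − (1 − p)(1 − q).

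| q | 100 mL | 250 mL | Difference (points) | Risk ratio |
|---|---|---|---|---|
| 0% | 5.0% | 30.0% | 25.0 | 6.00 |
| 10% | 14.5% | 37.0% | 22.5 | 2.55 |
| 20% | 24.0% | 44.0% | 20.0 | 1.83 |
| 30% | 33.5% | 51.0% | 17.5 | 1.52 |

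The difference shrinks by the factor (1 − q), and the ratio falls faster. The contrast is diluted, not removed.

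**The case against.** The case on the other side has four parts.

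- **Loose wording.** Section 6.1.3 states a datetime rule and section 6.1.4 lists onset datetime, so start date in 6.1.5 may be shorthand; 6.1.3 itself uses it that way. This is plausible. But 6.1.3 allocates events to study periods, while 6.1.5 states its own rule for this split, and a programmer may follow it literally.
- **The dosing-block reading.** The Period 1 and Period 2 tables support it, and for that split a date is nearly enough. The SAP's study-period figure and the protocol's List of Definitions were not available for this check, so a definition may exist there. Even so, 6.1.5 would be subdividing events by infusion period into during and after the same undefined term, and infusion-time events would stay pooled.
- **Other acute data.** SAP 6.3 summarises blood pressure at all timepoints during infusion (Table 14.3.3.1), change from same-day pre-dose at all post-dose timepoints (Table 14.3.3.2) and threshold categories (Table 14.3.3.3). This stands, and it limits the damage. It does not replace the event tables: reported events and measured values are different data, and SAP section 8 notes that the investigator decided which blood pressure values counted as events of special interest.
- **Uncertain data.** Protocol 8.4.1 asks only for the date of onset, and SAP 4.6 lists infusion rates by timepoint but no start and stop times. This stands, and the fix allows for it.

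A reader might infer from the 24-hour day that nearly all events labelled during are misclassified. That needs onsets spread evenly over the day, which the documents do not support: vital signs are collected during infusions, and the named risk is itself infusion-related. A reader might also infer that the acute dose or rate comparison fails. It does not: adverse event analysis is descriptive, no event-by-rate comparison is planned, and the measured blood pressure tables remain.

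**Conclusion.** The point holds as a weakness in one descriptive set of adverse event tables, worth correcting before database lock. The stated rule uses a date for a split whose natural meaning, under the protocol's use of the term, is a window of 2 to 3 hours. In that sense the during category takes in the whole calendar day, of which the infusion is 8.3 to 12.5%. In the dosing-block sense it takes in five or six days and never isolates infusion-time events.

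The consequence is dilution of unknown size. The table of assumed risks shows its direction and form only. The 2.5-fold difference in average rate holds only at equal infusion duration; within the permitted range it runs from 1.7 to 3.75. The acute blood pressure assessment as a whole survives through SAP 6.3.

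The conclusion assumes that 6.1.5 would be programmed as written and that no definition in the unavailable figure or definitions list settles the matter. If one does, the remaining task is to cite it in 6.1.5 and to say that onset time applies.

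**What to change.** In SAP 6.1.5 and the notes to Tables 14.3.1.7.1 to 14.3.1.7.3:

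1. Define infusion period explicitly, and use a different term for Period 1 and Period 2.
2. Replace event start date with AE onset datetime, compared with the start and stop datetime of that day's infusion, consistent with the 6.1.3 rule.
3. Use three classes: during infusion; after infusion stop, or between infusions, within the inpatient course; after discharge.
4. Show events with missing onset time in a separate row. Under the partial-date rule in 6.1.3 such an event can be assigned to more than one period, which would double-count it here.

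The cost is SAP wording and a modest programming change, if the data exist. Before database lock, confirm that the case report form holds AE onset time and infusion start and stop times. The downside is that some events will fall in the missing-time row; if many do, the split will be thin and should be reported with that caveat.

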6.2 Clinical Laboratory Evaluations

Numeric measurements of hematology, serum chemistry, urinalysis and urine chemistry will be investigated. Changes from baseline for all safety lab parameters will be summarized at each scheduled timepoint (Table 14.3.2.1.1-14.3.2.1.3). Frequency tables for categorical test results will be tabulated at each scheduled timepoint (Table 14.3.2.2). Shift tables from the baseline to each post-baseline scheduled timepoint will be presented (Table 14.3.2.3.1-14.3.2.3.3).

6.3 Vital Signs

Summary statistics will be presented for the actual values and change from baseline values (as appropriate) at each time point for all vital signs (Temperature, Pulse Rate, Systolic Blood Pressure (BP), Diastolic BP, Respiratory Rate) and weight. Changes from baseline for all vital sign parameters and weight will include pre-dose at Day 1 to pre-dose at subsequent days and at all timepoints during infusion (Table 14.3.3.1). In addition, changes from baseline for all vital sign parameters will include pre-dose at each infusion day to all post-dose timepoints within each infusion day (Table 14.3.3.2).

The incidence of the following categorized blood pressure values and changes from baseline will be summarized (Table 14.3.3.3):

- Systolic BP > 180
- Systolic BP > 200
- Systolic BP < 90
- Diastolic BP > 110
- Diastolic BP > 120
- Diastolic BP < 50
- An absolute change of >30% from Day 1 pre-dose (baseline) in systolic and/or diastolic BP. This change includes positive and negative percent changes.

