7.1.1.2.6 Targeted Physical Exams

While the subject is inpatient, a targeted physical exam, including auscultation of the heart and lungs, an assessment of peripheral edema, and weight, will be performed per the Study Schedule ([Section 7.3](#)).

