7.3.4 TREATMENT

There are two inpatient treatment periods scheduled during the trial, each with a total of 5 infusions. It is anticipated that sites will infuse subjects with 5 doses over 5 days. A “grace day” is allowed in the event of unanticipated safety or health concerns during each inpatient treatment period.

Visits 3-7 (Days 1-5) and 11-15 (Days 85*-89):

*Day 85 has a ± 7-day window. Visits 12-16 should follow consecutively.

- Perform the following procedures prior to administering study treatment:
 - Review AEs and concomitant medications
 - Obtain blood and urine samples for comprehensive laboratory panel; fasting samples preferred **(Visits 4, 6, 12, and 14 Only)**
 - Obtain samples for proteomics/epigenetics/biobanking; fasting samples preferred **(Visits 3 and 11 Only)**
 - Obtain i-STAT safety laboratory test samples and assess results before each infusion
 - Perform targeted physical exam (i.e. auscultation of heart and lungs and assessment of peripheral edema)
 - Measure and record the subject’s weight in kilograms
 - Perform 12-lead ECG **(Visit 11 Only)**
 - Ensure the subject has had an opportunity to eat a meal prior to cognitive and motor testing
 - Administer the Savonix Brief Battery
 - Perform ADAS-Cog/11 **(Visit 11 Only)**
 - Collect pre-infusion vital signs
- Administer study treatment and perform safety assessments per the Infusion Administration Manual
- Post-infusion: perform 12-lead ECG **(Visits 7 and 15 Only)**

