7.3.5 FOLLOW-UP

Visits 8 and 16 (Day 6 and Day 90 – Last Day of Inpatient Stay):

- Review AEs and concomitant medications
- Collect the following:
 - Vital signs and subject’s weight in kilograms
 - Blood and urine samples for comprehensive laboratory panel (fasting samples preferred)
 - Samples for proteomics/epigenetics/biobanking (fasting samples preferred)
 - i-STAT safety laboratory test samples and assess results before discharge
- Perform targeted physical exam (i.e. auscultation of heart and lungs and assessment of peripheral edema)
- Ensure the subject has had an opportunity to eat a meal prior to cognitive and motor testing
- Perform cognitive assessments in the following order:

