5.2 Exclusion Criteria	Added exclusion criteria pertaining to the C-SSRS administered at screening.	Subjects reporting active suicidal ideation with at least some intent to act in the past 6 months will be excluded from the trial for safety reasons.
5.2 Exclusion Criteria	Previously read: Prior hypersensitivity reaction to any human blood product or intravenous infusion; any known drug allergy. Now reads: Prior hypersensitivity reaction to any human blood product or intravenous infusion; any known clinically significant drug allergy.	Modified to be less restrictive, such that subjects with drug allergies deemed not clinically significant who meet all other eligibility criteria may be enrolled.
7.3.3	Added section to the Study Schedule so that	To allow sites flexibility as to when

Randomization	randomization may occur any time after confirmation of eligibility (following Baseline) but prior to the subject’s first infusion on Visit 3. Included a recommendation to randomize subjects at the start of Visit 3, as this may reduce the risk of randomizing a subject to treatment who discontinues/withdraws prior to Visit 3.	randomization occurs.
7 Study Procedures and Schedule / 17 Schedule of Events	UPCR to be performed at screening ONLY. Added the following urine tests as part of comprehensive labs: albumin/creatinine, sodium/creatinine, and potassium/creatinine. Removed stat urinalysis and amended the tests performed as part of the urinalysis for comprehensive labs.	Added additional testing for safety. Determined that stat urinalysis would not be necessary for guiding dosing decisions.
7 Study Procedures and Schedule / 17 Schedule of Events	Added a targeted physical exam prior to dosing on Visits 3-7 and 11-15; and prior to discharge on V8 and V16.	To assess for safety.
7 Study Procedures and Schedule / 17 Schedule of Events	Fasting lab samples are preferred for all visits except screening; amended the order of procedures on applicable visits accordingly.	Fasting samples are preferable for proteomics.
7 Study Procedures and Schedule / 17 Schedule of Events	Added ECGs to V7 (after dosing), V11 (prior to dosing), and V15 (after dosing).	To assess for safety.
7 Study Procedures and Schedule / 17 Schedule of Events	Added weight measurements prior to dosing on Visits 3-7 and 11-15; and prior to discharge on V8 and V16.	To assess for fluid retention during dosing based on changes in weight.

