2.3 Study Phase, Visit, and Day

The study is set up as shown above, along with assigned study period, visit, and day. In general, the baseline is defined as the last assessment before the first intake of the study medication unless otherwise specified. All scheduled assessments after first administration of study drug will be used.

Repeat/unscheduled assessments will not be used in descriptive statistics or any per-time point analyses but will be shown in listings as applicable. Pre-dose unscheduled assessments will be taken into account for baseline determination and post first dose unscheduled assessments will be taken into account for worst-case determination as applicable.

Reference date refers to the start date of the first study drug administration. All efficacy and safety assessments at all visits will be assigned a day relative to this date. The relative day will be defined as: visit date – reference date + 1 for visits on or after the reference date and visit date – reference date for visits before the reference date. Consequently, there is no 'Day 0' defined.

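### SAP 6.3 tabulates weight change only from Day 1, so no planned table shows the within-subject weight change during the second dosing course

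*SAP*

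**What the plan says.** **Collection.** Protocol 7.3.4, under "Visits 3-7 (Days 1-5) and 11-15 (Days 85*-89"), requires staff before each infusion to "Measure and record the subject’s weight in kilograms". Protocol 7.3.5 repeats the weight at discharge: "Visits 8 and 16 (Day 6 and Day 90 – Last Day of Inpatient Stay"). Protocol 7.1.1.2.6 places it in the inpatient targeted exam: "an assessment of peripheral edema, and weight, will be performed per the Study Schedule". No weight is scheduled at Visits 9 and 10.

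**Purpose.** The revision history entry that introduced these weights says "To assess for fluid retention during dosing based on changes in weight". It is used here only as the reason for a procedure that is still in the current schedule.

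**Timing of course 2.** "Day 85 has a ± 7-day window. Visits 12-16 should follow consecutively".

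**Analysis.** The general rule in SAP 2.3 is a single baseline: "the baseline is defined as the last assessment before the first intake of the study medication unless otherwise specified". SAP 6.3 applies it to weight in Table 14.3.3.1: "Changes from baseline for all vital sign parameters and weight will include pre-dose at Day 1 to pre-dose at subsequent days". SAP 6.3 then adds Table 14.3.3.2, which takes each infusion day's pre-dose value as the reference, but for vital sign parameters only. The list of tables in SAP section 10 agrees: the title of 14.3.3.1 mentions weight and that of 14.3.3.2 does not. The protocol's definition of vital signs (7.1.1.1.8) also leaves weight out. SAP 6.3 further summarises actual values at each time point.

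**The concern.** Each course has its own starting weight: Visit 3 for course 1 and Visit 11 for course 2. For course 1, the Day 1 reference gives exactly the quantity wanted. For course 2, the Day 85 pre-infusion weight is treated as one more post-baseline value, and the changes at Visits 12-16 are still counted from Day 1. Whatever happened to body weight over the preceding 12 weeks is then part of the figure.

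The arms differ in infused volume, 5 × 100 = 500 mL against 5 × 250 = 1,250 mL per course, so weight change within a course, by dose, is a natural descriptive comparison. In a small safety study its value lies in the spread and the extremes: how variable the gain was, and how large the largest was. For course 2 the planned tables show neither. The physical-examination tables in SAP 6.5 do not fill the gap, because they cover screening and Day 168 only.

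**Working it through.** **1. Calendar check.** The first day of Week 13 is 12 × 7 + 1 = Day 85, which matches the Schedule of Events.
- Day 1 to Day 85: 84 days = 12.0 weeks.
- With the ±7-day window, course 2 starts between Day 78 and Day 92, which is 77 to 91 days (11 to 13 weeks) after Day 1.
- Day 6 to Day 85, with no scheduled weight between them: 79 days.
- Day 85 to Days 86-90: 1 to 5 days.

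**2. What each reference measures.** Let d be the subject's true weight change from Day 1 to Day 85 (drift, including anything left over from course 1) and g the change from Day 85 to the course-2 visit. Ignoring measurement error:
- change from Day 1 = d + g
- change from Day 85 = g

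For g = +2 kg and d = −3, −2, −1, 0, +1, +2 kg, the Day 1 change at Day 90 is −1, 0, +1, +2, +3, +4 kg. The Day 85 change is +2 kg in every case.

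**3. What can be recovered from the planned table.** The mean of g is the mean Day 1 change at, say, Day 90 minus the mean Day 1 change at Day 85, exact only if the same subjects contribute to both rows. The variance is not recoverable: Var(g) = Var(change at Day 90) + Var(change at Day 85) − 2 × Cov, and the covariance is not tabulated. The same holds for the minimum and maximum, because the extremes of the two rows need not be the same subjects.

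**4. Illustrative size.** The documents give no SD for weight and no threshold for weight gain, so these inputs are assumptions: drift SD 1.5, 2.5 or 3.5 kg, measurement SD 0.5 or 0.8 kg, normal and independent, with 2 kg as an example gain.
- SD of change from Day 1 = √(drift SD² + 2 × measurement SD²)
- SD of change from Day 85 = √2 × measurement SD
- Chance of an apparent gain of 2 kg or more when g = 0: 1 − Φ(2 / SD)

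| Drift SD (kg) | Measurement SD (kg) | SD from Day 1 (kg) | SD from Day 85 (kg) | Apparent ≥2 kg with no gain, Day 1 | Same, Day 85 |
|---|---|---|---|---|---|
| 1.5 | 0.5 | 1.66 | 0.71 | 11.4% | 0.2% |
| 1.5 | 0.8 | 1.88 | 1.13 | 14.4% | 3.9% |
| 2.5 | 0.5 | 2.60 | 0.71 | 22.1% | 0.2% |
| 2.5 | 0.8 | 2.74 | 1.13 | 23.3% | 3.9% |
| 3.5 | 0.5 | 3.57 | 0.71 | 28.8% | 0.2% |
| 3.5 | 0.8 | 3.68 | 1.13 | 29.3% | 3.9% |

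In the first row, √(1.5² + 2 × 0.5²) = √2.75 = 1.66 and 1 − Φ(2/1.66) = 11.4%.

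**5. Share of the weights affected.** Leaving out the two starting weights, there are five inpatient weights in course 1 (Visits 4-8) and five in course 2 (Visits 12-16). The point concerns the second five.

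**The case against.** The strongest reply is that nothing is lost. SAP section 2 says the listings will carry all subject data points collected or derived, sorted by treatment group, site and subject. With about 20 subjects per arm, a marked course-2 gain can be read off by hand. Actual weights are summarised at each time point, and the Day 85 pre-dose row is itself in Table 14.3.3.1. Fluid overload is also watched directly: the targeted exam covers heart, lungs and edema before every infusion, clinically significant edema is an AESI (Protocol 8.4.3), and SAP 6.1.5 summarises AESIs per period. All of this stands, and it limits the point to a missing summary.

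It is also fair that one baseline before any drug is a standard choice and the only one that shows cumulative change. That is a reason to keep the Day 1 change, not a reason to omit the other. The wording of SAP 6.3 does not exclude a further analysis, and section 10 allows the output list to be modified, but no such output is listed now.

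Three stronger readings are tempting, and the documents do not support them:
- A reader might infer that course-2 fluid gain cannot be recovered at all. The listings and the Day 85 row contradict this.
- A reader might infer that weight gained at home would be reported as gained during course 2. The SAP does not label the Day 1 change that way, and such a gain already shows in the Day 85 row.
- A reader might extend the point to creatinine and eGFR, with Visit 10 as the course-2 reference. Visit 10 is Day 56 ± 7, about four weeks before course 2. It is not the last creatinine before course 2, because the i-STAT panel, which includes creatinine, is drawn before the Visit 11 infusion. The eGFR AESI is an absolute limit and needs no period baseline. The point is therefore confined to weight.

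**Conclusion.** The point holds for weight, as a gap in the tabulated summary. SAP 6.3 gives weight one reference, Day 1 pre-dose. At Visits 12-16 the tabulated change therefore mixes 77-91 days of drift with a course-2 change of 1 to 5 days. No planned table gives the SD, range or maximum of the within-subject course-2 change by dose, although detecting fluid retention during dosing is why the inpatient weights were added. Course 1 is not affected.

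That conclusion rests on the text and calendar arithmetic alone. The kilogram figures are illustrations on assumed SDs. They show that the Day 1 reference could blur individual course-2 gains substantially (SD 1.7-3.7 kg against 0.7-1.1 kg), and that measurement error remains under either reference. The consequence is modest, because the individual data are kept and edema is reported separately, but the improvement is nearly free and worth making before database lock.

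**What to change.** In SAP 6.3, keep the change from Day 1 and define for weight only a period baseline: the Visit 3 pre-infusion value for Visits 4-8 and the Visit 11 pre-infusion value for Visits 12-16. Add to Table 14.3.3.1 a panel with the change from period baseline by dose group (n, mean, SD, median, minimum, maximum) and each subject's maximum gain per course, summarised the same way. State that subjects without a Visit 11 weight do not contribute to the course-2 panel.

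The cost is a sentence or two in the SAP and one extra panel in an existing table. It needs no new data, visits or clinical rules. It also follows what the SAP already does elsewhere, since exposure, treatment completion and adverse events are summarised per period.
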